8.4.7 Sub-group analyses

The details of any analyses and selection of the prognostic factors and/or baseline characteristics will be pre-specified in the SAP or reported as ad hoc evaluations in the CSR.

8.5 Timing of analyses

8.5.1 Part A: safety lead-in cohort

A formal analysis of safety data will take place after 12 evaluable patients have completed the Cycle 1 DLT evaluation.

8.5.2 Part B: tumour specific expansion cohorts

A formal analysis of safety and efficacy data will take place in each expansion cohort when the target number of patients have completed at least two cycles of treatment. This will include an analysis of the biomarker data in the TNBC and SCLC cohorts to inform selection of further expansion cohorts.

8.5.3 Final analysis

The final analysis will take place when all expansion cohorts in Part B have completed patient enrolment and follow-up as per the CSP (see Section 4.2) or at an earlier time if the study is stopped for reasons of safety. At this time all analyses will be performed according to the SAP for the purpose of generating the CSR.

8.6 Evaluation and calculation of variables by AstraZeneca or delegate

8.6.1 Calculation or derivation of efficacy variable(s)

8.6.1.1 Tumour response rate

Patients will undergo regular tumour assessments until documented objective disease progression as defined by RECIST v1.1 ([Eisenhauer et al 2009](#)). At each restaging visit the RECIST data for a patient will be assigned a response of CR, PR, SD, or PD depending on the status of the disease compared with baseline and previous assessments (see [Appendix D](#)).

The objective response rate is defined as the number of the patients with a confirmed best overall response of CR or PR divided by the number of patients in the Full Analysis Set (FAS [see Section [8.2.2](#)]). Similarly, the disease control rate is defined as the percentage of FAS patients with a best overall response of CR or PR or SD.

Progression of Target Lesions (TL) will be calculated in comparison with what the tumour burden was at a minimum (i.e., smallest sum of diameters previously recorded on study). In the absence of progression, tumour response (CR, PR, or SD) will be calculated in comparison to the baseline tumour measurements obtained before starting treatment.

If a patient has had a tumour assessment that cannot be evaluated, then the patient will be assigned a visit response of non-evaluable (NE) (unless there is evidence of progression in which case the response will be assigned as PD).

For TL measurements, if $\leq 1/3$ of the TL sizes are missing (either not evaluable or not read, or the scan was not done) then a scaling up rule will be applied as follows:

- If $\leq 1/3$ of lesions recorded at baseline are missing, then the results will be scaled up (based on the baseline sizes) to give an estimated sum of diameters and this will be used in calculations (this is equivalent to comparing the visit sum of diameters of the non-missing lesions to the baseline sum of diameters excluding the lesions that are missing and determining at what rate the lesions are changing)
- If $> 1/3$ of lesions recorded at baseline are missing, then the target lesion response will be NE. However, if the sum of non-missing target lesion diameters would result in PD (i.e., if using a value of 0 for missing lesions the sum of diameters has still increased by $> 20\%$ or more compared with the smallest sum of diameters on study and has an absolute increase ≥ 5 mm) PD takes precedence over NE.
- A visit response of CR will not be allowed if any of the TL data are missing.

8.6.1.2 Progression-free survival

Progression-free survival is defined as the time from date of first dose of AZD1775 until the date of objective disease progression or death (by any cause in the absence of progression) regardless of whether the patient withdraws from therapy or receives another anti-cancer

therapy prior to progression. Patients who have not progressed or died at the time of analysis will be censored at the time of the latest date of assessment from their last evaluable RECIST assessment.

If the patient progresses or dies after two or more missed visits, the patient will be censored at the time of the latest evaluable RECIST assessment. If the patient has no evaluable visits or does not have baseline data they will be censored at 0 days unless they die within two visits of baseline.

Progression-free survival will be derived based on scan/assessment dates not visit dates. If RECIST assessments/scans contributing towards a particular visit are performed on different dates then the date of progression will be determined based on the earliest of the dates of the component that triggered the progression. With regard to censoring, a patient will be censored at the latest of the dates contributing to a particular overall visit assessment.

8.6.1.3 Changes in tumour size

Percent changes in tumour size from baseline will also be determined for patients with measurable disease at baseline and is derived at each visit as the % change in the sum of the diameters of Target Lesion (TLs) TLs. $\% \text{ change} = \frac{[(\text{post baseline TL sum} - \text{baseline TL sum}) / \text{baseline TL sum}] * 100$.

8.6.1.4 Duration of response

Duration of response is defined as the time from the date of first documented response until the date of documented progression or any cause death. In the case where a patient does not progress following response, the duration of response censoring time will be the same as the PFS censoring time.

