Bone lesions identified on an isotopic bone scan at baseline and confirmed by CT, MRI or X-ray at baseline should be recorded as NTL and followed by the same method as per baseline assessment.

In the D6130C00001 study isotopic bone scans may be used as a method of assessment to identify the presence of new bone lesions at follow-up visits. New lesions will be recorded where a positive hot-spot that was not present on the baseline bone scan assessment is identified on a bone scan performed at any time during the study. The Investigator should consider the positive hot-spot to be a significant new site of malignant disease and represent true disease progression in order to record the new lesion. Confirmation by CT, MRI and x-ray is recommended where bone scan findings are equivocal.

FDG-PET scan

In the D6130C00001 study FDG-PET scans may be used as a method for identifying new lesions, according with the following algorithm: New lesions will be recorded where there is positive FDG uptake* not present on baseline FDG-PET scan or in a location corresponding to a new lesion on CT/MRI at the same follow-up visit. If there is no baseline FDG-PET scan available, and no evidence of new lesions on CT/MRI scans then follow-up CT/MRI assessments should be continued, scheduled as per protocol or clinical indicated, in order to confirm new lesions.

*A positive FDG-PET scan lesion should be reported only when an uptake greater than twice that of the surrounding tissue is observed.

TUMOUR RESPONSE EVALUATION

Schedule of evaluation

Baseline assessments should encompass chest, abdomen and pelvis and should additionally investigate areas that may be involved based on signs and symptoms of individual patients and should be performed no more than 28 days before the start of study treatment. Follow-up assessments will be performed every 6 weeks +/- 1 week window interval after start of treatment until objective disease progression as defined by RECIST 1.1. or withdrawal from study. Any other sites at which new disease is suspected should also be adequately imaged at follow-up.

If an unscheduled assessment was performed and the patient has not progressed, every attempt should be made to perform the subsequent assessments at their scheduled visits. This schedule is to be followed in order to minimise any unintentional bias caused by some patients being assessed at a different frequency than other patients.

Target lesions (TL)

Documentation of target lesions

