To achieve 'unequivocal progression' on the basis of non-target lesions, there must be an overall level of substantial worsening in non-target disease such that, even in presence of SD or PR in target lesions, the overall tumour burden has increased sufficiently to merit discontinuation of therapy. A modest 'increase' in the size of one or more non-target lesions is usually not sufficient to qualify for unequivocal progression status.

New Lesions

Details of any new lesions will also be recorded with the date of assessment. The presence of one or more new lesions is assessed as progression.

A lesion identified at a follow up assessment in an anatomical location that was not scanned at baseline is considered a new lesion and will indicate disease progression.

The finding of a new lesion should be unequivocal: i.e. not attributable to differences in scanning technique, change in imaging modality or findings thought to represent something other than tumour.

If a new lesion is equivocal, for example because of its small size, the treatment and tumour assessments should be continued until the new lesion has been confirmed. If repeat scans confirm there is a new lesion, then the progression date should be declared using the date of the initial scan.

Symptomatic deterioration

Symptomatic deterioration is not a descriptor of an objective response: it is a reason for stopping study therapy.

Patients with ‘symptomatic deterioration’ requiring discontinuation of treatment without objective evidence of disease progression at that time should continue to undergo tumour assessments where possible until objective disease progression is observed.

Evaluation of Overall Visit Response

The overall visit response will be derived using the algorithm shown below.

Overall visit response

Target lesions	Non-Target lesions	New Lesions	Overall response
CR	CR	No	CR
CR	NA	No	CR
NA	CR	No	CR
CR	Non CR/Non PD	No	PR
CR	NE	No	PR
PR	Non PD or NE	No	PR
SD	Non PD or NE	No	SD
NE	Non PD or NE	No	NE
PD	Any	Yes or No	PD
Any	PD	Yes or No	PD
Any	Any	Yes	PD

CR = complete response, PR = partial response, SD = stable disease, PD = progressive disease, NE = not evaluable, NA = not applicable (only relevant if there were no NTLs at baseline).

CONFIRMATION OF RESPONSE

In the D6130C00001 study, imaging for confirmation of response (CR or PR) should be performed at next scheduled visit (certainly no less than 4 weeks) following the date the criteria for response were first met.

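### DoR takes its censoring from PFS only when the patient does not progress, so after two or more missed visits the same responder can be censored for PFS and an event for DoR

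*Protocol*

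**What the plan says.** Protocol Section 2.1 lists ORR, DCR, DoR and PFS as the Part B primary outcome measures. Sections 8.4.4 and 8.4.5 plan Kaplan-Meier displays of PFS and DoR for the expansion cohorts.

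Section 8.6.1.2 defines PFS as the "time from date of first dose of AZD1775 until the date of objective disease progression or death". It adds a missed-visit rule for anyone who "progresses or dies after two or more missed visits, the patient will be censored at the time of the latest evaluable RECIST assessment".

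Section 8.6.1.4 has two sentences. The first defines DoR as "the time from the date of first documented response until the date of documented progression or any cause death". The second covers censoring: "where a patient does not progress following response, the duration of response censoring time will be the same as the PFS censoring time". Neither mentions missed visits, and nothing else in the protocol carries the missed-visit rule into DoR.

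On the schedule, Appendix D states: "Follow-up assessments will be performed every 6 weeks +/- 1 week window interval after start of treatment". It asks for a response to be confirmed at the next scheduled visit, at least 4 weeks later. For patients who stop drug without progression, footnote n to Table 1 (Part A) sets follow-up every 12 weeks from the last dose. Footnote n to Table 2 (Part B) gives the same interval but words it for patients with progression. Section 4.3.2.1 sends patients who stop before progression to these tables.

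**The concern.** For a responder, PFS and DoR differ in where the clock starts. A reader expects them to stop on the same date with the same status. Here they need not. The trigger for borrowing PFS censoring is that the patient did not progress, whereas the relevant condition is that PFS was censored. The two conditions part company when progression is found after a long gap: PFS discards the gap, while DoR counts all of it as continued response and then records an event.

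At stake is the coherence of two primary outcome measures in small cohorts (Section 8.1 plans about 15 biomarker-positive and 15 biomarker-negative patients in each of TNBC and SCLC). The affected patients are those whose true progression time is least well known. A programmer following the text would produce listings in which a patient's response outlasts that patient's progression-free time.

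**Working it through.** The protocol gives no figure to reproduce, so the check applies the two rules as written.

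**Step 1: status of each kind of responder**

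| Responder | PFS (8.6.1.2) | DoR (8.6.1.4) |
|---|---|---|
| Alive, no progression | Censored at last evaluable assessment | Censored at the same time |
| Progression, no gap | Event | Event, same date |
| Progression after two or more missed visits | Censored at last evaluable assessment | Event at the late date |
| Death without progression, no gap | Event | Event by first sentence; second sentence points to a PFS censoring time that does not exist |
| Death without progression after two or more missed visits | Censored at last evaluable assessment | Event by first sentence; censored by second |

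The third row is a contradiction in status between the endpoints. The fifth is a contradiction within Section 8.6.1.4.

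**Step 2: size of the difference for one patient**

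Let s be the visit interval in weeks, r the week of first response, L the week of the last evaluable scan, and m the number of missed visits, with progression found at the visit after the gap.

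- Progression is found at week L + s(m+1).
- PFS is censored at L.
- DoR as written is an event at L + s(m+1) − r.
- The excess of DoR over PFS is s(m+1) − r, which is positive when r < s(m+1).

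*Illustration A, 6-weekly scans continue (s = 6).* Partial response at week 6, confirmed at week 12 (the last scan), weeks 18 and 24 missed. Progression is at 12 + 6 × 3 = week 30. PFS is censored at 12 weeks; DoR is an event at 30 − 6 = 24 weeks. The excess is 18 − 6 = 12 weeks. With the PFS rule carried across, DoR would be censored at 12 − 6 = 6 weeks.

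*Illustration B, 12-weekly visits after stopping drug near week 12 (s = 12).* Same response and last scan, weeks 24 and 36 missed. Progression is at 12 + 12 × 3 = week 48. PFS is censored at 12 weeks; DoR is an event at 48 − 6 = 42 weeks. With the PFS rule carried across, DoR would again be censored at 6 weeks.

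*When DoR does not exceed PFS.* With 6-weekly scans and two missed visits, the excess is 12 weeks for first response at week 6, 6 weeks for week 12, 0 for week 18 and −6 for week 24. The difference in status is present in all four cases.

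**Step 3: direction of the effect on the Kaplan-Meier median**

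Aligning the rules replaces a late event with an early censoring. Two sets of assumed data show that the median can move either way. In both, the gap patient is an event at 24 weeks as written and censored at 6 weeks once aligned.

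- Three responders, the others with events at 12 and 18 weeks. As written, S(12) = 0.67 and S(18) = 0.33, so the median is 18 weeks. Aligned, two remain at risk, S(12) = 0.50 and S(18) = 0, so the median is 12 weeks (15 if the midpoint convention is used).
- Four responders, the others with events at 30, 36 and 42 weeks. As written, S(24) = 0.75 and S(30) = 0.50, so the median is 30 weeks. Aligned, S(30) = 0.67 and S(36) = 0.33, so the median is 36 weeks.

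**The case against.** The best defence concerns intent. A responder who dies without progression and without a gap has not progressed, yet has a PFS event and so no PFS censoring time to borrow. The second sentence of Section 8.6.1.4 therefore makes sense only as shorthand for a patient without a PFS event. Read that way, a patient censored for PFS after missed visits is censored for DoR too, and both contradictions disappear. That is a plausible account of what the sponsor meant, but it is not what the sentence says.

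A second argument is that such detail belongs in the SAP, which is not at hand. Leaving DoR censoring to the SAP would have been acceptable. The protocol instead states a rule with its own trigger. An SAP that copies it inherits the fault, and one that aligns the endpoints departs from the protocol's wording.

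Third, Illustration A depends on 6-weekly scans continuing after drug is stopped. On 12-weekly follow-up from a last dose near week 12, progression at week 30 follows only one missed visit (week 24). The missed-visit rule does not apply, PFS is an event at 30 weeks and DoR an event at 24. This stands: the individual figures depend on a schedule on which the protocol is not clear. The mismatch itself does not, as Illustration B shows.

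Fourth, the reach is small. It takes a confirmed responder, at least two missed visits and then either a return with documented progression or a death. Section 4.3.2.1 ends PFS assessments at new cancer therapy, Section 8.3 plans no hypothesis tests, and Section 8.4.5 treats DoR as informational. This also stands, and it limits the weight of the point.

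**Conclusion.** The point holds as a rule with the wrong trigger. Followed literally, the protocol can give one responder a censored PFS and a DoR event, and it gives two answers for a responder who dies without progression after a gap. DoR can exceed the same patient's recorded PFS, by 12 weeks in Illustration A and by 42 − 12 = 30 weeks in Illustration B. These patients are constructed; the protocol does not say how many responders will have such gaps, and they are likely to be few.

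Two stronger readings should be resisted. A reader might infer that the rule inflates reported DoR, or that aligning it will make DoR look worse. The documents do not support a direction, because turning a late event into an early censoring can shorten or lengthen the median. A reader might also infer that DoR exceeds PFS in every such patient. It does so only when first response comes before week s(m+1): week 18 with two missed 6-weekly visits, week 36 with two missed 12-weekly visits. What occurs in every patient with progression documented after such a gap is the difference in event status.

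**What to change.** Replace the last sentence of Section 8.6.1.4 with: *The end of response is the same date, with the same event or censoring status, as used for the PFS endpoint, including censoring after two or more missed visits.* This settles progression after a gap and death after a gap together, and it leaves a death without a gap as an event in both endpoints.

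The cost is one sentence, with no new data or patients. A few DoR events become censored observations, and the reported median DoR may move in either direction.

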8.7 Calculation or derivation of safety variable(s)

8.7.1 Exposure to investigational product

The total time on study treatment, as well as total exposure to study treatment and the amount delivered relative to the intended amount will be summarised. The number of patients with pauses and reductions and the dose intensity of AZD1775 will also be summarised.

8.7.2 Adverse events, laboratory changes, vital signs

Safety profiles will be assessed in terms of AEs and laboratory data, vital signs, and ECG data that will be collected for all patients. Treatment-emergent AEs are defined as any AE which initiates on or after the first day of study drug up through 30 days after study drug discontinuation.

8.7.3 Other significant adverse events (OAE)

During the evaluation of the AE data, the Medical Monitor will review the list of AEs that were not reported as SAEs and other adverse events (OAEs). Based on the expert's

judgement, significant adverse events of particular clinical importance may, after consultation with the Medical Science Director, be considered OAEs and reported as such in the Clinical Study Report. A similar review of laboratory/vital signs/ECG data will be performed for identification of OAEs.

Examples of these are marked haematological and other laboratory abnormalities, and certain events that lead to intervention (other than those already classified as serious), dose reduction or significant additional treatment.

8.8 Calculation or derivation of pharmacokinetic variables

Pharmacokinetic analysis of plasma for AZD1775 concentration data will be performed by Covance on behalf of AstraZeneca. The actual sampling times will be used in the parameter calculations and PK parameters will be derived using standard non-compartmental methods

Where possible the following PK parameters will be determined for AZD1775

- C_{\max}
- C8hr
- Time to C_{\max} (t_{\max})
- Time of last detectable concentration (t_{last})
- Terminal half-life ($t_{1/2\lambda z}$)
- Area under the plasma concentration-time curve from zero to 8 hours ($AUC_{(0-8)}$), from zero to the time of the last measurable concentration ($AUC_{(0-t)}$), and from zero to 12 h ($AUC_{(0-12)}$).

Following the multiple dose part of the study (Day 3 or Day 10) the following additional parameters will be calculated

- Accumulation on day 3 or 10 compared to day 1 for C_{\max} and $AUC_{(0-12)}$
- C_{trough}

The C_{\max} and t_{\max} parameters will be determined by inspection of the concentration time profiles. Where possible the terminal elimination rate constant (λz) will be calculated by log-linear regression of the terminal portion of the concentration-time profiles where there are sufficient data and the terminal (elimination) half-life ($t_{1/2\lambda z}$) will be calculated as $\ln 2/\lambda z$. The area under the concentration-time curve up to the last quantifiable sample ($AUC_{[0-t]}$) and the $AUC_{(0-8)}$ will be calculated using the linear up, log down trapezoidal rule. Where appropriate, the $AUC_{(0-t)}$ will be extrapolated to infinity using λz to obtain AUC. The area under the concentration-time curve across the dosing interval, AUC_{ss} will be calculated using the linear

up, log down trapezoidal rule. The apparent clearance (CL/F following the single dose and CL_{ss}/F following multiple dosing) will be determined from the ratio of dose/AUC or dose/ AUC_{ss} . The volume of distribution (V_{ss} , V_{ss}/F or V_z/F) will be determined from the $MRT \times CL/F$ and/or the accumulation ratio (RAC) will be calculated as the ratio of the $AUC_{(0-8)}$ on Cycle 3 Day 1. The time dependency of the pharmacokinetics on multiple dosing will be assessed by the calculation of the ratio of $AUC_{(ss)}/AUC(\text{single dose})$.

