1.1.3 Pharmacokinetics

The PK data of AZD1775 following a single oral administration showed a moderate rate of absorption with a time of maximum concentration (T_{max}) occurring at 3 to 4 hours. Post-peak plasma concentrations declined essentially in a mono-exponential manner with a terminal half-life ($t_{1/2}$) in the region of 10 hours. Exposure as measured by maximum plasma drug concentration (C_{max}) observed after a dose and area under the curve (AUC)_{0-∞} increased in a dose-proportional manner over the dose range of 325 to 1300 mg. Following single (100 to

325 mg) and multiple dose administrations of AZD1775 (25 to 325 mg BID and 100 to 200 mg QD) with carboplatin, cisplatin, and gemcitabine, plasma exposure of AZD1775 was consistent with predictions based on the single-dose regimen. Preliminary investigation of drug-drug interactions in Study NCT00648648 suggest a 60% increase in the exposure of AZD1775 in the presence of aprepitant (moderate CYP3A4 inhibitor), but no effect with the concomitant administration of steroids (moderate CYP3A4 inducers). Preliminary studies also suggested that the Pre-marketed Oral Formulation (PMF) of AZD1775 was similar to that of the Fit-For-Purpose (FFP) formulation. Based on the preliminary comparison of the results of AZD1775 PK parameters at the 225 mg PK dose, PK estimates in Asian patients were 30-45% higher than in Western patients.

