7. INVESTIGATIONAL PRODUCT AND OTHER TREATMENTS

7.1 Identity of investigational product(s)

AZD1775 is available as dry-filled capsules containing 25 or 100 mg of drug substance. Additional information about the investigational product (IP) may be found in the IB.

All study drugs must be kept in a secure place under appropriate storage conditions. The IP label on the bottle and the IB specifies the appropriate storage.

Investigational product	Dosage form and strength	Manufacturer
AZD1775	25 or 100 mg capsules	AstraZeneca

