7.2 Dose and treatment regimens

AZD1775 will be taken by mouth in approximate 12 hour intervals over 3 days at the start of week 1 and 2 of each 21-day cycle (Days 1-3 and 8-10), for a total of 12 doses with each cycle (see [Figure 2](#)). Mandatory prophylactic anti-emetic therapy will be administered as described in Section [6.8.3.2](#).

AZD1775 should be taken with 8 ounces of water approximately 2 hours before and again 2 hours after food. If BID dosing and a patient misses one of the two daily doses according to schedule, the dose should be taken as soon as possible, but not more than 6 hours after the missed dose was scheduled. If greater than 6 hours, the missed dose should be skipped and the patient should take the next dose when scheduled.

[figure not shown]
If vomiting occurs after a patient takes the AZD1775 dose, the patient should be instructed not to retake the dose, but to wait until the next scheduled dose of AZD1775. If no dose is scheduled for the following day, the dose will not be 'made up'. If vomiting persists, the patient should contact the Investigator.

AZD1775 dosing compliance should be reviewed with the patient at the beginning of each new treatment cycle when study drug is dispensed. All patients will be required to complete a dosing diary, which must be returned to the clinic for review at each visit. The patient should be instructed to record each date and time the dose(s) were taken on the dosing diary. If a dose is missed, the reason must be noted in the diary. A copy of the dosing diary is provided in the study reference materials.

Patients should be advised to return any unused AZD1775 in the original bottles, in addition to returning any empty bottles.

Figure 2 **21-day cycle**
AZD1775 dosing schedule, 21-day cycle

Day of Cycle

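### Section 8.8 gives one formula, MRT × CL/F, for Vss, Vss/F and Vz/F of a drug taken only by mouth, so the reported volume would be misstated

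*Protocol*

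**What the plan says.** The volume rule is one sentence of protocol Section 8.8: "The volume of distribution", given as Vss, Vss/F or Vz/F, "will be determined from the $MRT \times CL/F$ and/or the accumulation ratio". From there the sentence runs on into an accumulation ratio based on AUC(0-8) at Cycle 3 Day 1.

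The same section supplies the other ingredients:

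- Apparent clearance "will be determined from the ratio of dose/AUC", or from dose/AUCss after multiple dosing. AUC here is the value extrapolated to infinity where appropriate.
- The terminal rate constant λz, where possible, "will be calculated by log-linear regression of the terminal portion of the concentration-time profiles".
- A general statement that "PK parameters will be derived using standard non-compartmental methods".

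The route is oral throughout. Section 7.1 says "AZD1775 is available as dry-filled capsules containing 25 or 100 mg of drug substance", and Section 7.2 says "AZD1775 will be taken by mouth in approximate 12 hour intervals over 3 days". No intravenous dosing is planned.

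Full profiles exist only in Part A (Section 5.3.1, Table 4): pre-dose, 1, 2, 4, 6, 8 and 12 h, on Cycle 1 Day 1 and on Cycle 1 Day 3 or Day 10. Part B takes a pre-dose sample and one at 2-4 h (Section 5.3.2, Table 5).

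**The concern.** MRT × CL gives Vss when MRT describes disposition only, as after an intravenous bolus. After an oral dose the observed MRT is disposition MRT plus mean absorption time (MAT). The sentence therefore goes wrong in three ways:

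1. **Vss/F.** MRT × CL/F equals Vss/F + MAT × CL/F. Section 8.8 mentions no correction for MAT, and there is no intravenous reference from which to obtain one.
2. **Vz/F.** Its definition is (CL/F)/λz, which is a different quantity. Both inputs are derived in the same paragraph but are not used for it.
3. **Vss without /F.** Bioavailability is unknown, so this cannot be identified from oral data alone.

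The section also does not say whether MRT is extrapolated to infinity, stopped at the last sample, or corrected for carry-over at steady state. Characterising PK is a secondary objective in both parts (Section 2.2). What is at stake is a volume reported under a name that does not match how it was computed, with an error whose direction the protocol leaves open.

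**Working it through.** The protocol states no numerical volume, MRT or clearance, so there is no figure to reproduce. The check asks what the stated formula returns when the true volume is known.

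**Inputs.** Section 1.1.3 gives Tmax "occurring at 3 to 4 hours", an essentially mono-exponential decline, and a terminal half-life of about 10 h. The sampling times are those of Table 4.

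**Model (assumption).** One compartment with first-order absorption, so that true Vss/F = Vz/F = V/F.

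- k = ln 2 / 10 = 0.0693/h, so disposition MRT = 1/k = 14.43 h.
- ka is solved from Tmax = ln(ka/k)/(ka − k), and MAT = 1/ka.
- With MRT to infinity, (MRT × CL/F)/(V/F) = (1/k + 1/ka) × k = 1 + k/ka.

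| Tmax | ka (/h) | MAT (h) | Oral MRT (h) | Ratio to true V/F |
|---|---|---|---|---|
| 3 h | 0.938 | 1.07 | 15.49 | 1.074 |
| 3.5 h | 0.750 | 1.33 | 15.76 | 1.092 |
| 4 h | 0.615 | 1.63 | 16.05 | 1.113 |

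This gives 7% to 11% too high. If the half-life is assumed to be 8 h the range is 10.2% to 15.8%; at 12 h it is 5.7% to 8.6%.

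**MRT truncated at 12 h.** MRT(0-12) is 5.80 h (Tmax 3 h) to 6.06 h (Tmax 4 h). Multiplied by k, this gives 0.40 to 0.42 of true V/F when CL/F uses AUC to infinity. If CL/F were also taken from AUC(0-12), the ratio would be 0.76 to 0.83. Truncation matters because about 47% to 49% of AUC lies beyond 12 h.

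**Uncorrected MRT within one 12 h interval at idealised steady state.** MRT is 5.51 to 5.63 h. Multiplied by k, the ratio is 0.38 to 0.39.

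**Part A sampling times.** This run used noise-free data, the linear-up log-down rule, extrapolation to infinity, and λz from the last three points (an assumption). MRT × CL/F gives 1.10 to 1.15 times true V/F, and (CL/F)/λz gives 1.01 to 1.05. Some 80% to 83% of AUMC is extrapolated.

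**If kinetics are not one-compartment (assumed examples).** Four two-compartment cases were run, with terminal half-life 8.2 to 12.6 h and MAT 0.8 to 2.0 h. For instance, with central volume 1, k10 = 0.2, k12 = 0.1, k21 = 0.1 (/h) and MAT = 1.0 h:

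- Vss/F = 1 + 0.1/0.1 = 2.0, and Vz/F = 3.41.
- MRT × CL/F = 2.0 + 1.0 × 0.2 = 2.2, which is 1.10 times Vss/F but 0.64 times Vz/F.

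Across the four cases the product exceeds Vss/F by 8% to 23% and lies between 0.60 and 1.04 times Vz/F.

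**The merged clause.** The accumulation ratio in this sentence uses AUC(0-8) on Cycle 3 Day 1 and names no denominator. The bulleted list in Section 8.8 instead compares Day 3 or Day 10 with Day 1, for Cmax and AUC(0-12). Tables 1, 2, 4 and 5 schedule no PK sampling on Cycle 3 Day 1.

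**The case against.** **Direction.** A reader might infer that the reported volume is simply overstated. The document does not support that. The 7% to 11% excess needs MRT to infinity and one-compartment kinetics. Section 8.8 does not say which MRT is meant, and other readings of it give values far too low. This objection stands, and the claim has to be that the volume is misstated.

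**Pooling.** A reader might also infer harm to comparisons with other AZD1775 studies, because Section 8.9 allows data to be combined. That section describes population PK and PK-pharmacodynamic modelling, in which volume is estimated from concentrations. A non-compartmental volume from Section 8.8 would not enter it. No weight is placed on pooling here.

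**Damaged text.** The sentence changes subject halfway, so an alternative volume formula may have been lost in drafting or in reading the PDF. This is possible and cannot be settled from the document. The formula that remains is still attached to all three names.

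**Standard methods.** The general commitment to non-compartmental methods would lead many analysts to compute Vz/F correctly. But the specific sentence contradicts the standard definition, and this is not a detail left to the SAP: the protocol fixes it.

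**Little to gain.** Volume is not among the bulleted parameters, comes only from Part A (about 12 evaluable patients, Section 8.1), and is tied to no endpoint, dose decision or cohort decision in the protocol. That stands. Nor is the corrected Vz/F strong: the last three samples span 6 h (12 − 6), or 0.6 of a 10 h half-life. Compared like with like on the Part A times, though, it is 1% to 5% off against 10% to 15% for the product, before assay error.

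**Conclusion.** The point holds as an error of definition. One product is assigned to three volumes, and for oral data it is not the definition of Vz/F, it exceeds Vss/F by MAT × CL/F when MRT is taken to infinity, and it cannot yield Vss.

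The numerical effect is conditional. It is about +7% to +11% with MRT to infinity, a half-life of about 10 h, Tmax of 3 to 4 h and one-compartment kinetics. It is about 0.4 of the true value if MRT is truncated at 12 h or left uncorrected at steady state. Against Vz/F with more than one compartment the sign is open, and those figures rest on assumed parameters.

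The consequence is small: a descriptive PK parameter from Part A profiles. The formulas for CL/F, λz and half-life are not affected. This is a wording correction worth making, not a threat to the trial's conclusions.

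**What to change.** In Section 8.8:

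1. State that Vz/F is calculated as (CL/F)/λz, where λz is estimable.
2. Delete Vss and Vss/F. Alternatively, report MRT × CL/F only from the single-dose profile, with MRT extrapolated to infinity, under a label saying that it includes absorption time.
3. Give the accumulation ratio its own sentence, with numerator, denominator and day, and reconcile it with the bullet comparing Day 3 or Day 10 with Day 1 on AUC(0-12). Check the source text for anything lost at the join.

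The cost is a few lines of text. No samples or visits are added, since λz and CL/F are already derived in that section.
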